5.3.2.2. Exposure

No imputation will be done for first dose date. Date of last dose of study treatment, if unknown or partially unknown, will be imputed as follows:

- If the last date of study treatment is completely missing and there is no EOT CRF page and no death date, the participant should be considered to be ongoing and use the data cutoff date for the analysis as the last dosing date; or
- If the last date of study treatment is completely or partially missing and there is EITHER an EOT CRF page OR a death date available (on or prior to the data cutoff date), then impute this date as the last dose date:
 - = 31DECYYYY, if only Year is available and Year < Year of min (EOT date, death date),
 - = Last day of the month, if both Year and Month are available and Year = Year of min (EOT date, death date) and Month < the month of min (EOT date, death date), or
 - = min (EOT date, death date), for all other cases.

5.3.2.3. Date of Death

Missing or partial death dates will be imputed based on the last contact date:

- If the date is missing it will be imputed as the day after the date of last contact
- If the day or both day and month is missing, death will be imputed to the maximum of the full (non-imputed) day after the date of last contact and the following:
 - Missing day: 1st day of the month and year of death;
 - Missing day and month: January 1st of the year of death.

5.3.2.4. Date of Start of New Anticancer Therapy

Incomplete dates for start date of new anticancer therapy (drug therapy, radiation, surgery) will be imputed as follows and will be used for determining censoring dates for antitumor activity analyses and in the derivation of the end of on-treatment period. PD date below refers to PD date by investigator assessment.

- The end date of new anticancer therapy will be included in the imputations for start date of new anticancer therapy. If the end date of new anticancer therapy is:
 - Completely missing then it will be ignored in the imputations below;
 - Partially missing with only year (YYYY) available then the imputations below will consider 31DECYYYY as the end date of the new anticancer therapy;
 - Partially missing with only month and year available then the imputations below will consider the last day of the month for MMMYYYY as the end date of the new anticancer therapy.
- For participants who have not discontinued study treatment at the analysis cutoff date, last dose of study treatment is set to the analysis cutoff date in the imputations below.
- If the start date of new anticancer therapy is completely or partially missing then the imputed start date of new anticancer therapy is derived as follows:
 - Start date of new anticancer therapy is completely missing.
Imputed start date = min [max(PD date +1, last dose of study treatment +1), end date of new anticancer therapy].
 - Only year (YYYY) for start of anticancer therapy is available.
IF YYYY < Year of min [max(PD date +1, last dose of study treatment +1), end date of new anticancer therapy] THEN imputed start date = 31DECYYYY.
ELSE IF YYYY = Year of min [max(PD date +1, last dose of study treatment +1), end date of new anticancer therapy].
THEN imputed start date = min [max(PD date +1, last dose of study treatment +1), end date of new anticancer therapy].
ELSE IF YYYY > Year of min [max(PD date +1, last dose of study treatment +1), end date of new anticancer therapy].
THEN imputed start date = 01JANYYYY.
 - Both Year (YYYY) and Month (MMM) for start of anticancer therapy are available.

IF

YYYY = Year of min [max(PD date + 1, last dose of study treatment +1), end date of new anticancer therapy], AND

MMM < Month of min [max(PD date + 1 day, last dose of study treatment +1 day), end date of new anticancer therapy].

THEN

imputed start date = DAY (Last day of MMM) MMM YYYY.

ELSE IF

YYYY = Year of min [max(PD date +1, last dose of study treatment +1), end date of new anticancer therapy], AND

MMM = Month of min [max(PD date +1 day, last dose of study treatment +1 day), end date of new anticancer therapy].

THEN

imputed start date = min [max(PD date + 1 day, last dose of study treatment +1 day), end date of new anticancer therapy]).

ELSE IF

YYYY = Year of min [max(PD date +1, last dose of study treatment +1), end date of new anticancer therapy], AND

MMM > Month of min [max(PD date +1 day, last dose of study treatment +1 day), end date of new anticancer therapy].

THEN

imputed start date = 01 MMM YYYY.

ELSE IF

YYYY < Year of min [max(PD date + 1, last dose of study treatment + 1), end date of new anticancer therapy].

THEN

imputed start date = DAY (Last day of MMM) MMM YYYY.

ELSE IF

YYYY > Year of min [max(PD date + 1, last dose of study treatment + 1), end date of new anticancer therapy].

THEN.

imputed start date = 01 MMM YYYY.

5.3.2.5. Other Dates

Imputation methods for other partial dates as follows:

- If the day of the month is missing for a start date used in a calculation, the first day of the month will be used to replace the missing date.
- If both the day and month are missing, the first day of the year is used.
- For stop dates, the last day of the month, or last day of the year is used if the day or day and month are missing, respectively.
- If the date is completely missing, no imputation will be performed.

5.3.3. Missing Toxicity Grade of Adverse Events

Prior to Study Treatment: If no toxicity grade is available or the grade is reported as unknown for an adverse event prior to the first study treatment, then Grade 1 will be assumed for purposes of defining a baseline grade.

In summaries which present maximum toxicity grade, the maximum of non-missing grades will be displayed. Missing grade will only be displayed for cases where a participant reported only one event and the grade is missing.

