2.1.1. Primary Estimand

The primary estimand is the incidence of adverse events from the time of first dose to 28 days post last dosing date or the date prior to initiation of a new anticancer therapy, whichever occurs first for all participants who receive at least one dose of dacitinib, regardless of dosing interruptions or dosing compliance. It includes the following 4 attributes:

- Population: Participants with metastatic Non-Small Cell Lung Cancer (NSCLC) with EGFR exon 19 deletion or exon 21 L858R substitution mutations as defined by the inclusion and exclusion criteria, and who receive at least one dose of dacitinib;
- Variable: Binary indicator of whether any AE occurred at least once;
- Intercurrent event(s): All data after the intercurrent event “initiation of a new anticancer therapy (-1 day)” or “treatment discontinuation (+28 days post last dosing date)” will be excluded. Dosing interruptions or dosing compliance are not considered as intercurrent event for this analysis;
- Population-level summary: Incidence of AEs defined as the number of participants with AEs from the time of first dose to 28 days post last dosing date or the date prior to initiation of a new anticancer therapy, divided by the number of participants in the Population.

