3. ENDPOINTS AND BASELINE VARIABLES: DEFINITIONS AND CONVENTIONS

3.1. Primary Endpoint

The primary endpoint is the incidence of AEs, defined as the number of participants with treatment-emergent adverse events (TEAEs) from the time of first dose to 28 days post last dosing date or the date prior to initiation of a new anticancer therapy, divided by the number of participants in the Safety Set (see [Section 4](#)).

An adverse event is considered treatment-emergent if any of the following apply:

- The event occurs on-treatment (defined in [Section 3.5](#)) and was not seen prior to the start of treatment.
- The event was seen prior to the start of treatment but increased in National Cancer Institute Common Terminology Criteria for Adverse Events (NCI CTCAE) v4.03 grade while on-treatment.

Treatment-emergent adverse events will be characterized by type, frequency, severity (as graded by the investigator according to NCI CTCAE version 4.03 and coded by the Sponsor using Medical Dictionary for Regulatory Activities [MedDRA]), timing, seriousness, and relationship to dacomitinib.

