6. ANALYSES AND SUMMARIES

6.1. Primary Endpoint(s)

6.1.1. Adverse Events

Analyses of adverse events will be conducted on the Safety Set and will include all data collected from the time of first dose to 28 days post last dosing date or the date prior to initiation of a new anticancer therapy, regardless of dosing interruptions or dosing compliance. All analyses will be based on treatment emergent events unless otherwise specified. Treatment emergent is defined in [Section 3.1](#). AEs not considered treatment emergent will be flagged in data listings.

A high level summary of adverse events will include the number and percent of participants with:

- Any Adverse Event;
- Serious AE;
- Adverse Events with CTCAE Grade 3-4;
- Grade 5 events;
- AEs associated with dose interruptions;

- AEs associated with dose reductions;
- AEs associated with withdrawal.

Additionally, the number of events reported for each of the categories above will be provided. Each unique adverse event at the Preferred Term (PT) level for a participant is included in the count.

Seriousness, toxicity grade, action taken (interruption, reduction, and withdrawal) are as reported by the investigator on the adverse event CRF.

Summaries by System Organ Class (SOC) and PT in decreasing frequency will be provided for:

- Treatment Emergent Events (All Causality);
- Treatment Emergent Events by Maximum Toxicity Grade (All Causality);
- Treatment Emergent Events (Treatment Related);
- Treatment Emergent Events by Maximum Toxicity Grade (Treatment Related);
- Serious Treatment Emergent Events (All Causality);
- Serious Treatment Emergent Events (Treatment Related).

An event will be considered treatment related if the investigator considered the event related to the study drug or if causality information is unknown.

The following summaries will be provided by PT only (ie, summaries will not include SOC) in decreasing frequency for:

- Treatment Emergent Events (All Causality) by Preferred Term and Maximum Toxicity Grade;
- Treatment Emergent Grade 3-5 Events (All Causality) by Preferred Term and Maximum Toxicity Grade;
- Treatment Emergent Adverse Events Leading to Dose Interruptions (All Causality);
- Treatment Emergent Adverse Events Leading to Dose Interruptions (Treatment Related);
- Treatment Emergent Adverse Events Leading to Dose Reductions (All Causality);
- Treatment Emergent Adverse Events Leading to Dose Reductions (Treatment Related);

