- Treatment Emergent Adverse Events Leading to Permanent Withdrawal of Study Drug (All Causality);
- Treatment Emergent Adverse Events Leading to Permanent Withdrawal of Study Drug (Treatment Related);
- Serious Treatment Emergent Events (All Causality); and
- Serious Treatment Emergent Events (Treatment Related).

Each participant will be counted only once within each SOC and PT.

As described in [Section 5.3.3](#), in case a participant has events with missing and non missing toxicity grades, the maximum of the non-missing grade will be displayed. Missing grade will only be displayed in the event that only one event has been reported for a participant and the grade is missing.

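### In the maximum-grade AE tables, a participant with two or more events in a row, all ungraded, has no category, so those tables may not reconcile with the grade-free ones

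*SAP*

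**What the plan says.** SAP 5.3.3 sets two rules for on-treatment events with no toxicity grade. First: "In summaries which present maximum toxicity grade, the maximum of non-missing grades will be displayed". Second: "Missing grade will only be displayed for cases where a participant reported only one event and the grade is missing".

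SAP 6.1.1 restates both. For mixed records, "in case a participant has events with missing and non missing toxicity grades, the maximum of the non-missing grade will be displayed". For the rest, "Missing grade will only be displayed in the event that only one event has been reported for a participant and the grade is missing".

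In SAP 6.1.1 the rules bear on the SOC/PT tables by maximum grade (all-causality and treatment-related) and on the PT-only table by maximum grade. The same section also plans summaries that do not use grade: a high-level row for "Any Adverse Event", and SOC/PT tables of treatment-emergent events, all-causality and treatment-related. Participants are counted once per SOC and once per PT.

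The primary estimand in SAP 2.1.1 uses a "Binary indicator of whether any AE occurred at least once". SAP 3.1 gives the primary endpoint as incidence, "defined as the number of participants with treatment-emergent adverse events (TEAEs) from the time of first dose", over the Safety Set.

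**The concern.** The Missing category depends on how many events the participant reported, while the tables are built row by row. Two gaps follow.

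- If a participant has several events in a row and none is graded, there is no known grade to display, and Missing is not permitted because there is more than one event.
- If the count is taken over the whole participant, a term whose only event is ungraded is lost from its row as soon as the participant has any other event, even a graded event under a different term.

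What is at stake is the severity breakdown. Protocol 9.6.1 and SAP 3.1 both name severity among the features by which AEs are to be described. For any affected term, the grade columns would sum to fewer participants than the grade-free table for the same term, and the SAP gives no explanation or footnote for the difference. The rule also departs, without a reason, from the default in SAP 5.2.10, which keeps missing observations in the denominator as a category of their own.

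**Working it through.** **The plan's own figure.** Protocol 9.2 gives a maximum standard error of 0.05 for the rate of any AE with 100 participants. Check: sqrt(0.5 × 0.5 / 100) = 0.05. It is reproduced, and nothing below changes it.

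**Applying the rule to each pattern.** The inputs are the two display rules in SAP 5.3.3 and 6.1.1. A and B are different preferred terms. The single-event condition is read in two ways: over the participant's whole record, or over the events in the row. An overall (any-event) row is assumed to be part of the table.

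| Events of one participant | Row | Per-participant reading | Per-row reading |
|---|---|---|---|
| One ungraded A | overall, A | Missing | Missing |
| Grade 2 A and ungraded A | overall, A | Grade 2 | Grade 2 |
| Two ungraded A | overall, A | no category | no category |
| Ungraded A and ungraded B | overall | no category | no category |
| | A, B | no category | Missing |
| Grade 2 A and ungraded B | overall, A | Grade 2 | Grade 2 |
| | B | no category | Missing |

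The third pattern, and the overall row of the fourth, fail under both readings. The PT rows of the fourth pattern and row B of the fifth fail only under the per-participant reading. The second pattern never fails.

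**Size per affected participant.** If k of 100 participants fall into no category in a row, the grade columns of that row sum to k fewer participants than the grade-free table: k/100, or k percentage points.

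**How many might be affected.** The documents do not give the frequency of ungraded events. Assume that each event is ungraded independently with probability q, and that each participant has m events under m different terms.

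- Expected loss from the overall row, either reading = 100 × q^m:
  - q = 1%, m = 2: 100 × 0.01² = 0.01 participants
  - q = 5%, m = 2: 100 × 0.05² = 0.25
  - q = 10%, m = 2: 100 × 0.10² = 1.0
  - q = 10%, m = 3: 100 × 0.10³ = 0.1
  - q = 10%, m = 5: 100 × 0.10⁵ = 0.001
- Expected participant-by-PT entries lost, per-participant reading only = 100 × m × q:
  - q = 1%, m = 2: 2 of 200 entries
  - q = 10%, m = 5: 50 of 500 entries

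Under the per-participant reading, the share of PT entries lost is simply q.

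**Effect on the primary endpoint.** In every pattern the participant has at least one AE and counts once in the any-AE numerator, so the loss is 0.

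**After the fix.** With Missing shown whenever all of a participant's events in a row are ungraded, every cell marked as having no category becomes Missing. The grade columns plus Missing then equal the grade-free count in every pattern.

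**The case against.** The strongest objection is that the per-participant reading is not what the authors meant. In SAP 6.1.1 the restriction directly follows the statement that participants are counted once within each SOC and PT, which points to the row as the unit. Taken over a whole record, the companion rule would also put the diarrhea grade in the rash row, which cannot be intended. This is a fair argument for the per-row reading, and the second gap should be presented only as a possible reading. But both sections attach the condition to the participant and neither mentions the row. The per-row reading also leaves the first gap open.

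A second objection is size. The protocol has investigators grade AEs under CTCAE, and Protocol 9.6.1 provides for each AE to be listed with its intensity, so ungraded events should be few and would remain visible. This stands, and it is why the point is minor.

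Two stronger readings are tempting, and the documents support neither:

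- A reader might infer that the primary endpoint is undercounted, since these tables sit under the primary-endpoint heading of SAP 6.1. The incidence is a yes/no indicator tabulated in summaries without grade, and the display rule governs only summaries by maximum grade. Grade does enter SAP 3.1 when deciding whether an event present before treatment has worsened, but that is a separate step which this rule does not touch.
- A reader might infer that every ungraded event removes the participant unless it was the only one. A participant with graded and ungraded events in the same row is still shown, at the highest known grade.

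**Conclusion.** The rule is wrong as written, in a limited way. A participant whose events in a row number two or more and are all ungraded has no category under either reading. On the literal per-participant wording, an ungraded term also disappears from its row whenever the participant has another event. The consequence is confined to the severity tables: each affected participant lowers the row by 1 percentage point at n = 100 relative to the grade-free table.

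The likely number is small. Under the assumed 1% to 10% of events ungraded and two events per participant, the overall row loses 0.01 to 1.0 participants per 100, and less with more events. Losses at PT level would be larger, but only on the per-participant reading. These figures rest on independence and on assumed inputs; ungraded events clustered within participants would raise the loss from the overall row. The SAP also does not say whether the maximum-grade tables carry a total column that includes ungraded events, which would make a shortfall visible without assigning those participants a category.

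This is a desirable wording correction. It does not threaten the trial's main result.

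**What to change.** Replace the missing-grade sentences for maximum-grade summaries in SAP 5.3.3 and in 6.1.1 with:

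> Within each row (overall, SOC or PT), a participant is shown at the maximum non-missing grade; if all of the participant's events in that row have missing grade, the participant is shown under Missing.

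This defines the unit as the row, closes both gaps, follows the default in SAP 5.2.10 and imputes nothing. The cost is one sentence in two places and the matching display logic in the maximum-grade tables. No new data are needed. The primary endpoint and its analysis do not change, so the condition in SAP Section 2 for reflecting a change in a protocol amendment is not met.

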6. ANALYSES AND SUMMARIES

6.1. Primary Endpoint(s)

6.1.1. Adverse Events

Analyses of adverse events will be conducted on the Safety Set and will include all data collected from the time of first dose to 28 days post last dosing date or the date prior to initiation of a new anticancer therapy, regardless of dosing interruptions or dosing compliance. All analyses will be based on treatment emergent events unless otherwise specified. Treatment emergent is defined in [Section 3.1](#). AEs not considered treatment emergent will be flagged in data listings.

A high level summary of adverse events will include the number and percent of participants with:

- Any Adverse Event;
- Serious AE;
- Adverse Events with CTCAE Grade 3-4;
- Grade 5 events;
- AEs associated with dose interruptions;

- AEs associated with dose reductions;
- AEs associated with withdrawal.

Additionally, the number of events reported for each of the categories above will be provided. Each unique adverse event at the Preferred Term (PT) level for a participant is included in the count.

Seriousness, toxicity grade, action taken (interruption, reduction, and withdrawal) are as reported by the investigator on the adverse event CRF.

Summaries by System Organ Class (SOC) and PT in decreasing frequency will be provided for:

- Treatment Emergent Events (All Causality);
- Treatment Emergent Events by Maximum Toxicity Grade (All Causality);
- Treatment Emergent Events (Treatment Related);
- Treatment Emergent Events by Maximum Toxicity Grade (Treatment Related);
- Serious Treatment Emergent Events (All Causality);
- Serious Treatment Emergent Events (Treatment Related).

An event will be considered treatment related if the investigator considered the event related to the study drug or if causality information is unknown.

The following summaries will be provided by PT only (ie, summaries will not include SOC) in decreasing frequency for:

- Treatment Emergent Events (All Causality) by Preferred Term and Maximum Toxicity Grade;
- Treatment Emergent Grade 3-5 Events (All Causality) by Preferred Term and Maximum Toxicity Grade;
- Treatment Emergent Adverse Events Leading to Dose Interruptions (All Causality);
- Treatment Emergent Adverse Events Leading to Dose Interruptions (Treatment Related);
- Treatment Emergent Adverse Events Leading to Dose Reductions (All Causality);
- Treatment Emergent Adverse Events Leading to Dose Reductions (Treatment Related);

- Treatment Emergent Adverse Events Leading to Permanent Withdrawal of Study Drug (All Causality);
- Treatment Emergent Adverse Events Leading to Permanent Withdrawal of Study Drug (Treatment Related);
- Serious Treatment Emergent Events (All Causality); and
- Serious Treatment Emergent Events (Treatment Related).

Each participant will be counted only once within each SOC and PT.

As described in [Section 5.3.3](#), in case a participant has events with missing and non missing toxicity grades, the maximum of the non-missing grade will be displayed. Missing grade will only be displayed in the event that only one event has been reported for a participant and the grade is missing.

6.2. Secondary Endpoint(s)

6.2.1. Overall Response Rate

Analysis of treatment effect based on Overall Response Rate (ORR) will be conducted on the Safety Set and will include all data collected from the time of first dose until disease progression, death or initiation of a new anticancer therapy, whichever occurs first, regardless of tolerability or duration on treatment.

ORR is defined as the percentage of participants with a best overall confirmed response of CR or PR according to RECIST v1.1. Participants without documented CR or PR will be considered as non-responders. The evaluation of ORR will be based on investigator assessment relative to the Safety Set.

ORR will be calculated along with the two-sided 95% CI using the Wilson's Score Method.

In addition, the frequency (number and percentage) of participants with BOR of CR, PR, SD, PD, non-CR/non-PD (applicable only to participants with non-measurable disease at baseline), and NE (not-evaluable) will be tabulated.

BOR will be assessed based on reported overall responses at different evaluation timepoints by the investigator from the date of first dose until documented disease progression or start of new anticancer therapy, according to the following rules:

- CR = at least two determinations of CR at least 4 weeks apart and documented before progression and start of new anticancer therapy
- PR = at least two determinations of PR or better (and not qualifying for a CR) at least 4 weeks apart and before progression and start of new anticancer

- SD (for participants with at least one measurable lesion at baseline) = at least one SD assessment (or better and not qualifying for CR or PR) \geq 6 weeks after date of first dose and before progression and the start of new anticancer therapy
- Non-CR/Non-PD (for participants with only non-target disease at baseline) = at least one Non-CR/Non-PD assessment (or better and not qualifying for CR) \geq 6 weeks after date of treatment start and before progression and the start of new anticancer therapy
- PD = progression \leq 13 weeks after date of first dose and not qualifying for CR, PR or SD
- Not Evaluable (NE) = all other cases.

Clinical deterioration will not be considered as documented disease progression.

Participants with BOR of NE will be summarized by reason for having NE status. The following reasons will be used:

- Early death (defined as death prior to 6 weeks after date of first dose);
- No post-baseline assessments, for reasons other than early death;
- All post-baseline assessments have overall response NE;
- New anticancer therapy started before first post-baseline assessment;
- SD of insufficient duration (< 6 weeks after first dose);
- PD too late (> 13 weeks after first dose).

Special and rare cases where BOR is NE due to both early SD and late PD will be classified as 'SD of insufficient duration'.

